7.2 Study enrolment

7.2.1 Selection of patients for recruitment and enrolment

At each site, patients (or parents/guardians on behalf of minors) will be invited to participate in the study when they present with fever to the participating health facilities for care.

Health centre staff will work with study staff to identify patients who present with fever.

Study staff will screen and enrol participants according to the selection criteria listed in section 6. A total of 2400 patients will be enrolled at each site (see sample size calculations in section 11.3), with approximately half being outpatients and half inpatients. If a patient is enrolled as an outpatient but deteriorates clinically and is admitted to hospital within <24 hours after enrolment, the patient will be re-classified as an inpatient for study purposes. If a patient is enrolled as an outpatient and then admitted ≥ 24 hours after enrolment, s/he will remain listed as an outpatient for study data purposes.

Since the causes of fever are likely to be different in children and adults, enrolment will be stratified so that participants are enrolled in two age groups of approximately equal numbers: children aged two months (≥ 2 months) to <15 years, and those aged 15 years and older. In addition, so that results accurately represent the patient population at each site, site-specific recruitment strategies will be developed to achieve enrolment of a random sample of patients presenting throughout the day and week (including those presenting after hours or at weekends, who may come from areas further from the health facility, and/or have more severe presenting symptoms) and over the course of the 12-month

recruitment period. In each of the four categories defined by age and in-/outpatient status, 12 consecutive patients per week will be recruited. The day of the week that recruitment starts will be rotated. There may be slight variations on this strategy due to site specific constraints. The total number of patients presenting to the hospital with fever each day (or week), including those not in the study, over the course of the study period will be recorded.

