11.1 Quantitative outcome measures and analysis

Listed by study objective:

- 1) To determine the treatable and/or preventable causes of fever in children and adults presenting as outpatients, and among those admitted to hospitals, in areas represented by the study sites;

For outpatients the attributable fraction (AF) will be calculated for each pathogen or group of pathogens. This will be done separately for each site and age stratum. For each group of patients, the odds ratio (OR) for the association between each pathogen and fever will be calculated by comparing cases and controls. Logistic regression will be used to calculate the odds ratio. In order to take the matched design into account, strata based on geographical location and season will be defined at each site and the analysis will be adjusted for age, sex and stratum. Since cases and controls are recruited at a constant rate throughout the year but fever incidence is likely to vary by season, the analysis will be weighted by the proportion of patients included in the study of the total number of cases seen at the study

site in the given season. AF will then be calculated as $AF_A = p_A(1-OR_A)$. Confidence intervals will be calculated in an appropriate way, e.g. bootstrapping or delta method.

For inpatients, first the distribution of diagnoses in each site will be tabulated for all inpatients in the study. Then a second analysis to calculate AFs will be carried out for inpatients, but this will be restricted to inpatients who come from the same geographical area as the controls. The calculation of AFs for inpatients may be dropped if insufficient numbers of in-patients come from the same area as the controls.

- 2) To determine how fever aetiology varies according to patient age, level of the health system, geographical area, local malaria and HIV prevalence, and other risk factors;

Stratified analyses will be carried out as above to estimate the AF for sub-groups of patients.

- 3) To determine the prevalence and spectrum of antimicrobial resistance among bacterial pathogens identified in clinical specimens from febrile patients;

At each site the proportion of bacterial pathogens with antimicrobial resistance defined by standardized criteria will be calculated. The proportion of common organisms demonstrating resistance to a standard panel of antibiotics will be reported.

Specific secondary objectives:

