1) To generate data on incidence of specific infections among study participants, and therefore contribute key data on disease burden for some infections that are not counted in current “global burden of disease” estimates;

For an area whose population size is known, a health utilization survey will be used to estimate r , the proportion of fevers for which treatment was sought at a study centre. The total number of cases seen at the study site from the defined population will be multiplied by $1/r$, to obtain the total cases in a year from the defined population. This will be divided by the size of the population to estimate incidence. Incidence of fever caused by specific pathogens will be calculated by multiplying the incidence by the AF for that pathogen.

3) Evaluation of available biomarker assays to assess their performance and potential utility in fever case management in the study areas;

The sensitivity, specificity, and positive and negative predictive value of each biomarker will be estimated.

4) To generate data to support the development of new fever case management algorithms which may be evaluated in future studies;

The association between the presence of pathogens with predefined clinical and other variables will be examined.

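### The outpatient attributable-fraction analysis is weighted by the sampling fraction itself, so the high-fever season counts least when it should count most

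*Protocol*

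**What the plan says.** For primary objective 1, protocol Section 11.1 estimates an AF for each pathogen among outpatients, by site and age stratum. It uses the prevalence among cases, p_A, and an odds ratio from a logistic regression adjusted for age, sex and strata of location and season. The reason given for weighting is: "Since cases and controls are recruited at a constant rate throughout the year but fever incidence is likely to vary by season". The rule that follows is that "the analysis will be weighted by the proportion of patients included in the study of the total number of cases seen at the study" site, taken season by season. No other section states an inverse.

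Section 7.2.1 gives the recruitment scheme: "In each of the four categories defined by age and in-/outpatient status, 12 consecutive patients per week will be recruited". Its stated aim is "so that results accurately represent the patient population at each site". It also plans to record the denominator: "The total number of patients presenting to the hospital with fever each day (or week), including those not in the study".

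The AF is used again under secondary objective 1: "Incidence of fever caused by specific pathogens will be calculated by multiplying the incidence by the AF for that pathogen".

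For inpatients, Section 11.1 says that "first the distribution of diagnoses in each site will be tabulated for all inpatients in the study". An AF analysis follows, limited to inpatients from the controls' area. The inpatient paragraph does not mention weights.

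**The concern.** The protocol sees the problem correctly. A fixed weekly quota takes a small share of patients in a busy season and a large share in a quiet one, so the enrolled sample under-represents the busy season. The usual remedy is to let each enrolled patient stand for N/n patients seen. The sentence instead names n/N as the weight, which shrinks the contribution of the busy season a second time.

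If the rule is followed, p_A is pulled towards the low-season value for any infection whose share of fever cases changes with the caseload. The AF is built on p_A. The incidence estimate multiplies a whole-year fever incidence by that AF, which is only valid if the AF represents all cases seen in the year. Primary objective 1 and secondary objective 1 are therefore both exposed.

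**Working it through.** **The plan's own figures.** The protocol gives no numerical example of the weights. Its quota is consistent with its sample size: 12 × 52 = 624 per category a year, against the 600 per group in Section 11.2. Section 11.2 also gives ±1.7 points for a 5% prevalence with 600 patients, and 1.96 × √(0.05 × 0.95 / 600) = 1.74 points agrees.

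**Inputs.** From the protocol: a constant quota, so about n = 300 per half-year season in a group of 600. Assumed, because the protocol gives no figures: two seasons of equal length, a high:low caseload ratio R of 2 to 4, and the pathogen prevalences among cases shown below. I set N = 1000 in the low season and 1000R in the high season; only the ratio matters.

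**Formula.** Weighted prevalence = Σ n_s w_s p_s / Σ n_s w_s. The target is Σ N_s p_s / Σ N_s.

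- Weight N/n: each term becomes N_s p_s, so the target is recovered exactly.
- No weight: each season counts one half.
- Weight n/N as written, with n constant: each term is proportional to p_s / N_s.

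The high season's share is therefore R/(1+R) in truth, 1/2 unweighted and 1/(1+R) as written. The unweighted share misses the truth by (R−1)/(2(R+1)) and the written one by (R−1)/(R+1), which is twice as much.

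**Results.** The fractions n/N (high, low) are 0.15 and 0.30 at R = 2, 0.10 and 0.30 at R = 3, and 0.075 and 0.30 at R = 4.

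| Caseload | Prevalence high / low | True (= N/n weights) | Unweighted | As written |
|---|---|---|---|---|
| 2:1 | 7% / 3% | (2×7+3)/3 = 5.7% | 5.0% | (0.15×7+0.30×3)/0.45 = 4.3% |
| 3:1 | 15% / 5% | (3×15+5)/4 = 12.5% | 10.0% | (0.10×15+0.30×5)/0.40 = 7.5% |
| 4:1 | 20% / 2% | (4×20+2)/5 = 16.4% | 11.0% | (0.075×20+0.30×2)/0.375 = 5.6% |

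**Carry-over to AF and incidence.** The AF is p_A times a function of the odds ratio. If the odds ratio is the same in all seasons, the AF, and then the incidence, is wrong by the same factor as p_A: 4.33/5.67 = 0.76, 7.5/12.5 = 0.60 and 5.6/16.4 = 0.34 in the three rows.

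**Limits on direction.** A pathogen more common in the low season would be overstated instead of understated. With more than two seasons, the result that the written weights do worse than none holds when prevalence rises or falls steadily with caseload; an irregular pattern would need its own calculation. A pathogen with no seasonal variation among cases is unaffected.

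**Precision cost of the right weights.** The Kish design effect is mean(w²)/mean(w)². For 2:1 it is 2.5/2.25 = 1.11, and for 4:1 it is 8.5/6.25 = 1.36.

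**The case against.** The strongest reply is that this is loose wording. The stated purpose only makes sense with inverse weights, so the authors may well have meant them, and a statistical analysis plan that is not shown may say so. That is plausible, and it limits any claim that the final results will be biased. It does not rescue the sentence: the protocol does not leave the weight open but names one, and an analyst who follows it reverses the correction.

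A second reply concerns scope. The weighting sentence follows the logistic regression, and the protocol does not say whether p_A is weighted. Season is among the adjustment strata, so an odds ratio constant across seasons would hardly move. This stands, and it is why the point is about p_A and what is built on it. If p_A were left unweighted it would still miss the target, by half as much in the two-season case.

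A third reply concerns size. The larger examples use strong seasonality, while Section 11.2 expects any single pathogen to be rare. In the mild example the gap is 5.67 − 4.33 = 1.3 points, inside the ±1.7 points of Section 11.2. That is fair as to size. But the error is systematic, does not shrink with more patients, and runs the same way for every infection that peaks in the busy season.

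A reader might also infer that the inpatient tabulation is wrong because no weight is mentioned, that it pools children and adults, or that the fever tally cannot supply denominators by category. The documents do not support these as errors. They are silent on weighting that table and on splitting the tally, which an analysis plan or operating procedure could settle, and Section 11.2 already lists inpatient children and inpatient adults as separate analysis groups.

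**Conclusion.** The weight stated in Section 11.1 is the inverse of the one needed. Given the constant quota in Section 7.2.1, it gives least weight to the busiest season, and this follows from the rule without any assumption about disease.

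The size is not known from the protocol. Under two equal seasons, the error in p_A runs from about 1.3 points (5.7% against 4.3%) with mild seasonality, through 5.0 points (12.5% against 7.5%), to 10.8 points (16.4% against 5.6%) with strong seasonality.

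The finding is confined to the stated outpatient weight. It does not show that the odds ratios are reversed or that every AF is biased. For inpatients the only consequence is conditional: if their results are meant to represent all febrile inpatients over the year, the same reason for weighting applies, because they are recruited under the same quota.

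**What to change.** Replace the sentence in Section 11.1 with a rule that each case is weighted by the inverse of the sampling fraction (total cases seen divided by cases included), by season within site, age group and in-/outpatient category. State that these weights apply to p_A, and say whether they also enter the logistic regression and what weight controls carry. Use the same weights wherever inpatient results are meant to represent the year's febrile inpatients.

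The total seen should be counted, as far as possible, among patients who meet the same eligibility criteria. Section 6 excludes outpatients living outside the catchment area or with diarrhoeal symptoms, and adult outpatients with lower respiratory symptoms. If the excluded share changes with season, a raw fever count distorts the weights; if it is constant, the relative weights are unaffected. The exclusion reasons, age and residence that Section 7.2.1 records for screened patients can help here.

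The cost is a wording change, plus keeping an already planned count by category and, where feasible, by eligibility. The statistical price is a modest loss of precision: a design effect of about 1.1 at a 2:1 caseload and 1.36 at 4:1 for two seasons, and more if finer periods make the weights more variable.

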6 STUDY POPULATION AND SELECTION CRITERIA

Participants will be patients who present with fever for health care at the selected health care facilities. Patients of all ages two months and older will be eligible for enrolment. Study sites include outpatient and inpatient facilities in Laos, Malawi, Mozambique, Myanmar, and Zimbabwe. Patients will be recruited if they fulfil all of the following criteria (see also section 7.2 on participant enrolment, and Screening and Enrolment Forms [Appendix C]):

- 1) Tympanic or axillary temperature $\geq 37.5^{\circ}\text{C}$ at presentation;
- 2) Not having been hospitalized or having undergone surgery in the previous month;
- 3) Age ≥ 2 months (two months or older);
- 4) For outpatients, residence (at the time of enrolment) within the defined catchment area around the health facility (see section 7.5.1);
- 5) For outpatients aged ≥ 15 years, absence of symptoms of lower respiratory infection and of diarrhoeal diseases as defined by:
 - a) cough AND ≥ 1 of the following: cough productive of green/yellow sputum, or haemoptysis;
 - b) ≥ 3 loose stools within the previous 24 hours;
- 6) For outpatients aged ≥ 2 months to < 15 years, absence of symptoms of diarrhoeal diseases as defined by: ≥ 3 loose stools within the previous 24 hours;
- 7) Willingness and ability to provide demographic and clinical information, and clinical samples, at the time of enrolment and 28 days later;
- 8) Provision of written informed consent for adult participants; or for children, provision of written consent from a parent/guardian and assent from the child (according to local regulations and practices at each study site).

Controls will be community members in the study site health facilities' catchment areas, frequency matched to participants by age and season (see section 7.5 for details of selection and study activities for community controls).

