Patients who are not enrolled in the study will be managed according to routine practice by health facility staff. For those patients who are screened and excluded, the reason for exclusion will be recorded, along with the patient's age, sex, and location of usual residence. At each site where HIV testing will be performed (i.e., where HIV prevalence in the general adult population is >1%), HIV counselling and testing is linked to an established treatment program. Other acute or chronic conditions are managed on-site as capacity allows, or referred to a higher level of the health care system according to local guidelines.

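### The outpatient seasonal weight counts all cases seen, including patients section 6 bars from enrolment, so pooled attributable fractions can be mis-weighted by season

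*Protocol*

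**What the plan says.** Protocol section 11.1, primary objective 1, calculates the outpatient AF by site and age stratum from the case prevalence and an odds ratio adjusted for age, sex and strata of location and season. It then adds that "the analysis will be weighted by the proportion of patients included in the study of the total number of cases seen at the study" site, season by season. The reason given is that "cases and controls are recruited at a constant rate throughout the year but fever incidence is likely to vary by season". Section 7.2.1 is the source of the constant rate: "12 consecutive patients per week will be recruited" in each of the four age by in-/outpatient categories.

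The load count is also in section 7.2.1: "The total number of patients presenting to the hospital with fever each day (or week), including those not in the study". No split by eligibility, age group or in-/outpatient status is mentioned.

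Section 6 limits who can be enrolled. Outpatients aged 15 or over must have "absence of symptoms of lower respiratory infection and of diarrhoeal diseases as defined by" two items: cough together with "cough productive of green/yellow sputum, or haemoptysis", and three or more loose stools in 24 hours. Outpatients under 15 need only "absence of symptoms of diarrhoeal diseases as defined by" the same stool count. Outpatients must also live in the catchment area, which section 7.5.1 sets to hold about 80% of outpatients. No participant may have been in hospital or had surgery in the previous month.

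For patients screened and excluded, section 7.2.1 says that "the reason for exclusion will be recorded, along with the patient's age, sex, and location of usual residence". Section 11.1 does not use this log in the weight.

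**The concern.** A seasonal weight of this kind should restore the real seasonal mix of the population that was sampled, because a fixed weekly quota over-represents quiet seasons and under-represents busy ones. For that it needs the number of patients in each season who could have been enrolled. The stated denominator is larger, by a factor that depends on how many febrile outpatients are ineligible in that season. If diarrhoea or productive cough is itself seasonal, the weight partly follows illnesses that are not in the study.

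The outpatient AF is the specified analysis for primary objective 1, and secondary objective 1 multiplies it by fever incidence. A mis-weighting would pass into both. It would not show in a bootstrap or delta-method interval, and it would not shrink with more patients. The effect can differ between adults and children, because the cough exclusion applies only from age 15.

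**Working it through.** **Plan figures.** The protocol gives no figure for the weights, the seasonal load or the ineligible share. As a yardstick, its precision statement in section 11.2 reproduces: 1.96 × √(0.05 × 0.95 / 600) = 1.74 points, printed as 1.7.

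**Which count is the denominator.** Section 11.1 uses the same wording, total cases seen at the site, under secondary objective 1, as the input to all-fever incidence. There it adds a restriction to the defined population; in the weighting sentence it adds none. Section 7.5.4 describes the incidence input as the total cases of fever that present to the sites.

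**General form.** In season s let E_s be the eligible outpatients, x_s the ineligible share of all fever outpatients seen, and T_s = E_s / (1 − x_s) the total seen. With equal enrolment per season and inverse-fraction weights, season s should count in proportion to E_s but counts in proportion to T_s. The ratio of the two is 1 / (1 − x_s). If x_s is the same in every season it cancels. If the pathogen's prevalence and AF do not vary by season, the weights do not matter.

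**Illustration 1, prevalence (all inputs assumed).** Fevers seen: 1000 wet, 500 dry. Eligible: 90% in the dry season (450); 80%, 70% or 60% in the wet (800, 700, 600).

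- Wet:dry weight on all fevers: 1000/500 = 2.0. On eligible patients: 800/450 = 1.78, 700/450 = 1.56, 600/450 = 1.33.
- Cause present in 10% of wet-season and 2% of dry-season cases. All-fever weight: (100 + 10)/1500 = 7.33%. Eligible weight: (80 + 9)/1250 = 7.12%; (70 + 9)/1150 = 6.87%; (60 + 9)/1050 = 6.57%. Differences: +0.21, +0.46, +0.76 points (+3%, +7%, +12%).
- Cause present in 2% wet and 10% dry. All-fever weight: (20 + 50)/1500 = 4.67%. Eligible weight: 61/1250 = 4.88%; 59/1150 = 5.13%; 57/1050 = 5.43%. Differences: −0.21, −0.46, −0.76 points (−4%, −9%, −14%).

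**Illustration 2, AF (all seasonal inputs assumed).** Equal eligible load in two seasons; case prevalence 12% in season 1 and 5% in season 2; controls 5%. The 12% and 5% are borrowed from section 11.2. AF is taken as p(1 − 1/OR). The printed p(1 − OR) is negative for OR above 1; that is a separate matter.

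- Season 1: OR = (0.12/0.88)/(0.05/0.95) = 2.59, so AF = 0.12 × (1 − 1/2.59) = 7.37%. Season 2: OR = 1, AF = 0. Eligible weights: 0.5 × 7.37 = 3.68%.
- All-fever weights, by ineligible share in seasons 1/2:

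| Ineligible share | Weight of season 1 | Pooled AF | Relative error |
|---|---|---|---|
| 20%/20% or 40%/40% | 0.500 | 3.68% | 0 |
| 30%/20% | 0.533 | 3.93% | +7% |
| 40%/20% | 0.571 | 4.21% | +14% |
| 20%/40% | 0.429 | 3.16% | −14% |
| 50%/10% | 0.643 | 4.74% | +29% |
| 10%/50% | 0.357 | 2.63% | −29% |

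**Direction of the weight.** Section 11.1 literally weights by the included proportion, not its inverse. Taken literally, the all-fever wet:dry weight is 0.5 and the eligible one at 80% is 450/800 = 0.5625. The wet-season cause is then (0.5 × 10 + 2)/1.5 = 4.67% against (0.5625 × 10 + 2)/1.5625 = 4.88%. The gap has the same size and the opposite sign.

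**The case against.** **The wording may mean eligible cases.** The same passage uses cases for study patients, and section 7.2.1 never says that its count feeds the weights. This is possible but not the natural reading, given how section 11.1 uses the phrase for incidence. If eligible cases are meant, the text should say so.

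**It is detail for the analysis plan.** The mechanics of weighting often are. Here, however, the protocol states the denominator, so the point concerns a stated rule and not an omission.

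**All fevers may be the target.** Section 7.2.1 wants results that represent the patient population, and the AF is later applied to overall fever incidence. But ineligible outpatients have no chance of enrolment. Weighting up to them assumes that they share the enrolled patients' aetiology within each season, and nothing in the protocol supports that.

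**The effect is small.** This largely stands. A shift of 0.2 to 0.8 points is well inside sampling error: 1.96 × √(0.0733 × 0.9267 / 600) = 2.1 points at 7.3% prevalence, before any loss from weighting. Because the odds ratio is adjusted for season strata, the error acts mainly through the pooled prevalence, and through the odds ratio only if that differs by season.

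**Stronger readings the documents do not support.** A reader might infer that wet-season or respiratory causes will be over-stated. The protocol gives no seasonal shares, and the sign reverses with the direction of the weight. A reader might also infer that the information needed is lost. It is not: the screening log holds exclusion reason and age.

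**Conclusion.** The point holds as a correctable mismatch between the stated denominator and the population that could be enrolled. It biases the pooled prevalence and AF only when the ineligible share and the pathogen's contribution both vary by season. Section 5 expects causes of fever to vary by season, which makes this plausible but does not establish it. Neither direction nor size can be derived from the protocol. With the assumed loads and eligible shares and inverse-fraction weights, the prevalence shift is about 0.2 to 0.8 points (3–14% relative). The wider AF errors in the second illustration rest on more extreme assumed contrasts and are not estimates for these sites. The point merits a change because the rule is explicit, the error would be systematic, and a better rule is cheap. It does not invalidate the outpatient analysis.

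**What to change.** In section 11.1, define the weight for each enrolled outpatient as the estimated number of eligible febrile outpatients in that season and age group, divided by the number enrolled in it. Estimate the eligible number as the outpatient fever count times the share of screened outpatients who met all section 6 eligibility criteria, including residence, from the section 7.2.1 log. This also makes the weight explicitly the inverse of the sampling fraction; the present wording has the fraction itself.

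In section 7.2.1, record the fever count by age group and in-/outpatient status, and make sure the screening log can be tabulated the same way. Settle this before recruitment, because an unsplit tally may be hard to recover later.

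Under secondary objective 1, state that the AF applies to eligible outpatients when it is multiplied by all-fever incidence. The new weight does not remove that mismatch.

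The cost is a few sentences, a split tally at each site and a tabulation of the log. The weights become slightly more variable where few patients are screened in a period. The method also relies on the screened patients being a fair sample of febrile outpatients, which the recruitment scheme already aims for.

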11.2 Sample size considerations

Any single pathogen or aetiology is assumed to be likely to be rare in the study populations.^{2,14,15} To identify causes of fever, a sample size of 600 patients per group will enable estimation of the prevalence of an infection whose true prevalence is 5% with a precision of +/- 1.7% with 95% confidence, and to estimate the prevalence of an infection whose true prevalence is 1% with a precision of +/- 0.8% (see Table 3).

Table 3. Sample size estimates for varied infection prevalences

Number of participants	Prevalence	Confidence interval
600	5%	+/- 1.7
600	2%	+/- 1.1
600	1%	+/- 0.7

Since blood cultures and convalescent samples will not be taken from community controls, the prevalence of respiratory viruses (e.g., influenza and RSV) detected by polymerase chain reaction (PCR), and of baseline seropositivity to other pathogens, will be compared in cases and controls. The prevalence of respiratory viruses, and of seropositivity to common causes of fever, is assumed to be approximately 5% in the general population. A sample of 600 outpatients and 300 controls will provide >90% power to show a significant difference between a prevalence of 12% in cases and 5% in controls. Therefore, 600 febrile patients will be enrolled in each of four analysis groups (children aged ≥ 2 months to <15 years as inpatients and outpatients, and inpatients and outpatients aged ≥ 15 years), for a total of 2400 patients per site; plus 300 controls in each of the two age groups at each site (total 600).

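### The attributable fraction in section 11.1 is written with 1 − OR instead of 1 − 1/OR, so a pathogen positively associated with fever gets a negative fraction

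*Protocol*

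**What the plan says.** Protocol section 11.1, under primary objective 1, sets the AF as the outpatient measure: "For outpatients the attributable fraction (AF) will be calculated for each pathogen or group of pathogens". It is computed separately by site and age stratum. The odds ratio is defined in the usual direction: "the odds ratio (OR) for the association between each pathogen and fever will be calculated by comparing cases and controls". It comes from a weighted logistic regression adjusted for age, sex and a location-and-season stratum. The rule follows: "AF will then be calculated as $AF_A = p_A(1-OR_A") (the closing bracket follows the quoted words). The confidence interval is to come from the bootstrap or the delta method. The symbol p_A is not defined.

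The same AF is used in three further places in section 11.1:

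- a second inpatient analysis, restricted to inpatients from the controls' area, which may be dropped if numbers are too small;
- primary objective 2: "Stratified analyses will be carried out as above to estimate the AF for sub-groups of patients";
- secondary objective 1: "Incidence of fever caused by specific pathogens will be calculated by multiplying the incidence by the AF for that pathogen".

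No other section of the protocol gives a different or corrected formula.

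**The concern.** An OR above 1 marks a pathogen that is commoner in febrile cases than in controls, that is, a candidate cause of fever. For any positive p_A, the factor 1 − OR is then negative. The written rule therefore gives candidate causes a negative share of fevers and gives a positive share to pathogens that are rarer in cases.

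The AF is the reason for much of the control arm. Section 3.1.2 criticises earlier studies for having no controls and hence no AFs. Section 7.5.1 allows extra controls to sharpen the estimates for primary objective 1 and secondary objective 1. An error in this one expression passes into the AFs, their intervals and the incidence estimates. Section 10.4 says that the study protocols will be made freely available, so others could also copy the formula.

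**Working it through.** **Inputs.** Section 11.2 plans the case-control comparison as follows: "A sample of 600 outpatients and 300 controls will provide >90% power to show a significant difference between a prevalence of 12% in cases". The control prevalence in that comparison is 5%. This is the background level, which "is assumed to be approximately 5% in the general population". The protocol gives no worked AF, so its power figure is the only stated result that uses these prevalences.

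**Reproducing the power figure.** The significance level is not stated for this comparison, and two-sided 0.05 is assumed.

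- Pooled prevalence = (600 × 0.12 + 300 × 0.05)/900 = 0.0967.
- Standard error under no difference = √[0.0967 × 0.9033 × (1/600 + 1/300)] = 0.0209.
- Standard error under the alternative = √[0.12 × 0.88/600 + 0.05 × 0.95/300] = 0.0183.
- Power = Φ[(0.07 − 1.96 × 0.0209)/0.0183] = 94.4%, or 92.7% with continuity correction.

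Both agree with the stated figure of more than 90%. The power does not use the AF formula.

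**Odds ratio at the planning values.** OR = (0.12/0.88)/(0.05/0.95) = 2.59.

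**AF as written, p_A(1 − OR_A).**

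- p_A as case prevalence: 0.12 × (1 − 2.59) = −0.191.
- p_A as control prevalence: 0.05 × (1 − 2.59) = −0.080.

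**AF as it should be, p_A(1 − 1/OR_A), with p_A the case prevalence.** 0.12 × (1 − 1/2.59) = +0.0737.

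**Cross-check with Levin's form on control prevalence p₀.** p₀(OR − 1)/[1 + p₀(OR − 1)] = 0.05 × 1.59/(1 + 0.05 × 1.59) = +0.0737, the same value.

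**Other odds ratios, with p_A = 12% as case prevalence:**

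| OR | As written | Correct |
|---|---|---|
| 0.5 | +0.06 | −0.12 |
| 1 | 0 | 0 |
| 2 | −0.12 | +0.060 |
| 5 | −0.48 | +0.096 |
| 10 | −1.08 | +0.108 |

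At OR = 10 the written value is below −100%.

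**Incidence.** Multiplying fever incidence by the AF gives −19.1 instead of +7.4 pathogen-specific episodes per 100 fever episodes at the planning values.

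**Dropping the minus sign.** p(OR − 1) equals p(1 − 1/OR) × OR. At the planning values it gives 19.1% instead of 7.4%, too large by a factor of 2.59. It can also misrank causes. With illustrative values, p = 2% and OR = 10 gives 18%, ahead of p = 12% and OR = 2 at 12%. The correct AFs are 1.8% and 6.0%.

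**The case against.** The strongest defence is that this is a misprint. The surrounding text describes a standard case-control AF, and a negative result for each positively associated pathogen would be noticed at the first run. A reciprocal might also have been lost when the PDF was read. A misprint is likely, and the expression should be compared with the source file. But a lost reciprocal is not shown: the text is intact, and the inline 1/r under secondary objective 1 in the same section survived. A misprint in a stated rule still needs correcting, and the obvious quick repair, changing the sign, gives plausible but inflated numbers.

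Three limits on reach stand.

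- A reader might infer that every cause of fever gets a negative AF. Section 7.5.3 excludes blood culture, convalescent sera and urine from controls. Causes identified only by those tests have no case-control OR, and the formula cannot be applied to them.
- A reader might infer that the ranking of causes is reversed. That holds at equal p_A with ORs above 1, but not in general. Take p = 0.20 with OR = 2, and p = 0.05 with OR = 10. The written values are −0.20 and −0.45, and the correct ones are +0.10 and +0.045, so the order is unchanged. The order can be distorted, but it is not systematically reversed.
- The AF is not the only output of primary objective 1. For inpatients, about half of enrolment (section 7.2.1), the first analysis is a tabulation of diagnoses.

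It is also fair to say that −19.1% and +7.4% rest on reading p_A as case prevalence. Under the control-prevalence reading, p_A(1 − 1/OR_A) would not be the right expression either, and Levin's form would be needed.

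**Conclusion.** The formula is wrong as written. The sign error is algebraic and does not depend on the meaning of p_A, the significance level or the sample size. It affects the outpatient AFs and the area-restricted inpatient AFs of primary objective 1, the subgroup AFs of primary objective 2, and the pathogen-specific incidence of secondary objective 1. This applies to pathogens tested in both cases and controls.

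It does not affect the sample size, the inpatient tabulations, the resistance proportions, or causes found only by tests not done in controls. The size at the planning values uses the crude odds ratio of 2.59. The protocol does not show that anyone has computed the AF this way, and no analysis code or statistical analysis plan was available to check. The point concerns the rule stated in section 11.1.

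**What to change.** In section 11.1:

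- replace the expression with AF_A = p_A(1 − 1/OR_A);
- define p_A as the weighted pathogen prevalence among cases and OR_A as the adjusted odds ratio;
- base the bootstrap or delta-method interval on that expression;
- confirm that the analysis code, and the statistical analysis plan if there is one, use the same form, not p_A(OR_A − 1).

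The subgroup AFs and the incidence calculation refer back to this definition and need no further change. The cost is a one-line correction, two definitions and a code check. No data collection, sample size or participant procedure changes.
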